## STATEMENT OF COMPLIANCE

The trial will be conducted in accordance with International Conference on Harmonisation Good Clinical Practice (ICH GCP), applicable United States (US) Code of Federal Regulations (CFR), and the IBTC contractual terms. The Principal Investigator will assure that no deviation from, or changes to the protocol will take place without prior agreement from the Investigational New Drug (IND) sponsor and documented approval from the Institutional Review Board (IRB), except where necessary to eliminate an immediate hazard(s) to the trial participants. All personnel involved in the conduct of this study have completed Human Subjects Protection and ICH GCP Training.

The protocol, informed consent form(s), recruitment materials, and all participant materials will be submitted to the IRB for review and approval. Approval of both the protocol and the consent form must be obtained before any participant is enrolled. Any amendment to the protocol will require review and approval by the IRB before the changes are implemented to the study. All changes to the consent form will be IRB approved; a determination will be made regarding whether a new consent needs to be obtained from participants who provided consent, using a previously approved consent form.

## 1 PROTOCOL SUMMARY

### 1.1 SYNOPSIS

Title:	A Phase 0 Study of infigratinib in Recurrent High-Grade Glioma (HGG) Participants Scheduled for Resection to Evaluate Central Nervous System (CNS) Penetration with PK triggered expansion cohort		
Study Description:	
This trial is an open-label, multicenter, Phase 0 trial that will enroll up to 20 participants with recurrent high-grade glioma with FGFR1 K656E or FGFR3 K650E mutation or FGFR3-TACC3 translocation which are scheduled for resection. In the lead-in cohort, a total of 20 participants will be enrolled into the proposed phase 0 clinical trial. Participants will be administered infigratinib prior to surgical resection of their tumor.
 
Phase 0:
 
The Phase 0 study will include treatment of recurrent high-grade glioma participants with 125 mg of infigratinib 7 days prior to surgical resection.
 
To assess the PK and PD endpoints listed, blood, CSF and brain tumor tissue will be collected intraoperatively on Day 7 (enhancing and non-enhancing tumor tissue will be collected and analyzed separately). Additionally, blood samples will be obtained on Day 7 at pre-dosing (trough level), 0.5, 1, 2, 4, 6, 8, and 24 hours post dose. (Note: 24 h blood sample on Day 8).
 
Expansion Cohort:
 
Participants with tumors demonstrating PK-response will continue treatment with the same dose continuously for 21 days in 28-day cycles after surgery. A positive PK response will be unbound concentrations of infigratinib reaching 5-fold higher than cell-free biochemical IC50 within the non-enhancing region of the tumor. PD biomarkers will be included for exploratory analyses. Participants in the expansion cohort will return to the clinic to monitor safety per the schedule of events until treatment is ended and will be contacted approximately every 3 months by letter or phone for collection of survival data. The start of follow up for long-term survival begins following completion of the Day 30 safety follow up call.
 
Participants will be treated until unacceptable toxicity is observed, or until disease progression as assessed by radiographic or clinical metrics.
		
Primary Objectives/Endpoints	1. Phase 0: To measure the pharmacokinetic (PK) effects of infigratinib in recurrent high-grade glioma participants.	1. Phase 0: Total and Unbound infigratinib concentration in enhancing and non-enhancing tumor tissue (8hr), plasma (0-24H) and CSF (8hr) will be determined.	2. Expansion Cohort: Examine progression-free survival in recurrent high-grade glioma
		2. Expansion Cohort: 6-month progression-free survival (PFS6)	

A Phase 0 Study of Infigratinib in Recurrent Glioblastoma Patients  
Protocol 2020-08

	participants with demonstrated PK effects	rate measured from time of surgery to date of recurrence
Secondary Objectives/Endpoints	
 
1. Phase 0: PD Analysis
 
2. Expansion cohort: To monitor safety and tolerability of study drug in participants with recurrent high-grade glioma.
 
	
 
1. Phase 0: percentage of pERK+, MIB-1+ and Cleaved Caspase 3+ cells from the surgical tissue will be quantified and compared to baseline archival/biopsy tissue.
 
2. Expansion cohort: Safety and tolerability: 
 
a. Drug-related toxicity
 
b. Number of Adverse Events through study completion, assessed up to 60 months
 
c. Treatment-emergent adverse events (TEAEs)
 
d. Deaths
 
e. Clinical laboratory abnormalities per CTCAE (Version 5.0)
 
 
 

Exploratory Objectives/Endpoints	
 
1. Phase 0: Describe systemic PK
 
2. Expansion Cohort: Examine Overall Survival (OS) in recurrent high-grade glioma participants with demonstrated PK effects
 
	
 
1. Phase 0: Systemic plasma PK profile parameters (<math>T_{max}</math>, <math>C_{max}</math>, <math>t_{1/2}</math>, <math>AUC_{0-24h}</math>) for total and unbound levels will be determined for infigratinib.
 
2. Expansion Cohort Efficacy: 
 
a. Median Overall Survival (OS) from time of surgery to date of death from any cause
 
 
 

Study Population:	Participants undergoing resection for a recurrent high-grade glioma. Each participant must meet all the following inclusion criteria and none of the exclusion criteria to be eligible for study entry:	
Inclusion Criteria:	
 
1. Prior resection of histologically diagnosed high-grade gliomas (III and IV) defined as participants who have progressed on or following standard (Stupp regimen) therapy, which included maximal surgical resection, temozolamide, and fractionated radiotherapy.
 
2. Recurrence must be confirmed by diagnostic biopsy with local pathology review or contrast-enhanced MRI.
 
3. Have measurable disease preoperatively, defined as at least 1 contrast-enhancing lesion, with 2 perpendicular measurements of at least 1 cm, as per RANO criteria.
 
	

A Phase 0 Study of Infigratinib in Recurrent Glioblastoma Patients

Protocol 2020-08

	
 
4. Sufficient archival or biopsy tissue available to confirm eligibility.
 
5. Archival or biopsy tissue must demonstrate: FGFR1 K656E or FGFR3 K650E mutation or FGFR3-TACC3 translocation from NGS sequencing or IHC and RT-PCR.
 
6. Ability to understand and the willingness to sign a written informed consent document (personally or by the legally authorized representative, if applicable).
 
7. Has voluntarily agreed to participate by giving written informed consent (personally or via legally authorized representative(s), and assent if applicable). Written informed consent for the protocol must be obtained prior to any screening procedures. If consent cannot be expressed in writing, it must be formally documented and witnessed, ideally via an independent trusted witness.
 
8. Willingness and ability to comply with scheduled visits, treatment plans, laboratory tests and other procedures.
 
9. Age <math>\geq 18</math> at time of consent.
 
10. Have a performance status (PS) of <math>\leq 2</math> on the Eastern Cooperative Oncology (Group (ECOG) scale (Oken et al. 1982).
 
11. Ability to swallow oral medications.
 
12. Has adequate bone marrow and organ function as defined by the following laboratory values (as assessed by the local laboratory for eligibility):
 
								
	
Adequate bone marrow function:
 
 
 absolute neutrophil count	<math>\geq 1,000/\text{mcL}</math>	
 
 Platelets (at time of surgery)	<math>\geq 100,000/\text{mcL}</math>	
 
 hemoglobin	<math>\geq 8.0 \text{ g/dL}</math> Participants may receive erythrocyte transfusions to achieve this hemoglobin level at the discretion of the investigator.	
 
	absolute neutrophil count	$\geq 1,000/\text{mcL}$	Platelets (at time of surgery)	$\geq 100,000/\text{mcL}$	hemoglobin	$\geq 8.0 \text{ g/dL}$ Participants may receive erythrocyte transfusions to achieve this hemoglobin level at the discretion of the investigator.		
absolute neutrophil count	$\geq 1,000/\text{mcL}$								
Platelets (at time of surgery)	$\geq 100,000/\text{mcL}$								
hemoglobin	$\geq 8.0 \text{ g/dL}$ Participants may receive erythrocyte transfusions to achieve this hemoglobin level at the discretion of the investigator.								
	
Adequate hepatic and renal function:
 
 
 total bilirubin	<math>\leq 1.5 \times \text{ULN}</math>. Participants with Gilbert's syndrome with a total bilirubin <math>\leq 2.0</math> times ULN and direct bilirubin within normal limits are permitted.	
 
 AST(SGOT)	<math>\leq 3 \times \text{institutional ULN}</math>	
 
 ALT(SGPT)	<math>\leq 3 \times \text{institutional ULN}</math>	
 
 Calculated or measured creatinine clearance	<math>\geq 45 \text{ mL/min}</math>	
 
	total bilirubin	$\leq 1.5 \times \text{ULN}$ . Participants with Gilbert's syndrome with a total bilirubin $\leq 2.0$ times ULN and direct bilirubin within normal limits are permitted.	AST(SGOT)	$\leq 3 \times \text{institutional ULN}$	ALT(SGPT)	$\leq 3 \times \text{institutional ULN}$	Calculated or measured creatinine clearance	$\geq 45 \text{ mL/min}$
total bilirubin	$\leq 1.5 \times \text{ULN}$ . Participants with Gilbert's syndrome with a total bilirubin $\leq 2.0$ times ULN and direct bilirubin within normal limits are permitted.								
AST(SGOT)	$\leq 3 \times \text{institutional ULN}$								
ALT(SGPT)	$\leq 3 \times \text{institutional ULN}$								
Calculated or measured creatinine clearance	$\geq 45 \text{ mL/min}$								
	
Other Lab Values:
 
 
 Amylase or lipase	<math>\leq 2 \times \text{institutional ULN}</math>	
 
	Amylase or lipase	$\leq 2 \times \text{institutional ULN}$						
Amylase or lipase	$\leq 2 \times \text{institutional ULN}$								

A Phase 0 Study of Infigratinib in Recurrent Glioblastoma Patients  
Protocol 2020-08

	
calcium or phosphorus, or calcium-phosphorus product
 
<math>\leq 55 \text{ mg}^2/\text{dL}^2</math>
 
a. Inorganic phosphorus within normal limits b. Total corrected serum calcium within normal limits
 
13. Confirmed negative serum pregnancy test (<math>\beta</math>-hCG) before starting study treatment or participant is no longer of childbearing potential due to surgical, chemical, or natural menopause.
 
14. For females of reproductive potential: use of highly effective contraception for at least 1 month prior to screening and agreement to use such a method during study participation and for an additional 3 months after the end of treatment administration.
 
15. For males of reproductive potential: use of condoms or other methods to ensure effective contraception with partner and for an additional 1 month after the end of treatment administration. A condom is required to be used also by vasectomized men as well as during intercourse with a male partner to prevent delivery of the drug via seminal fluid.
 
16. Agreement to adhere to Lifestyle Considerations (see Section 5.3) throughout study duration.
 
17. Participants who received chemotherapy must have recovered (Common Terminology Criteria for Adverse Events [CTCAE] Grade <math>\leq 1</math>) from the acute effects of chemotherapy except for residual alopecia or Grade 2 peripheral neuropathy prior to Day 1. A washout period of at least 21 days is required between last chemotherapy dose and Day 1 (provided the patient did not receive radiotherapy).
 
18. Participants who received radiotherapy must have completed and fully recovered from the acute effects of radiotherapy. A washout period of at least 14 days is required between end of radiotherapy and Day 1.

Exclusion Criteria:	
 
1. Have a history of liver transplant.
 
2. Have impairment of gastrointestinal (GI) function or GI disease that may significantly alter the absorption of oral infigratinib (e.g., ulcerative diseases, uncontrolled nausea, vomiting, diarrhea, malabsorption syndrome, small bowel resection).
 
3. Known active systemic bacterial infection (requiring intravenous [IV] antibiotics at time of initiating study treatment), fungal infection, or detectable viral infection (such as known human immunodeficiency virus positivity or with known active hepatitis B or C [for example, hepatitis B surface antigen positive]). Screening is not required for enrollment.
 
4. Have a history and/or current evidence of extensive tissue calcification including, but not limited to, the soft tissue, kidneys, intestine, myocardium, vascular system, and lung with the exception of calcified lymph nodes, minor pulmonary parenchymal calcifications, and asymptomatic coronary calcification.
 
5. Have current evidence of corneal or retinal disorder/keratopathy including, but not limited to, bullous/band keratopathy, inflammation
 

	
or ulceration, keratoconjunctivitis confirmed by ophthalmic examination. Subjects with asymptomatic ophthalmic conditions assessed by the investigator to pose minimal risk for study participation may be enrolled in the study.
 
6. Have current evidence of endocrine alterations of calcium/phosphate homeostasis, e.g., parathyroid disorders, history of parathyroidectomy, tumor lysis, tumoral calcinosis etc.
 
7. Have had a recent (<math>\leq 3</math> months prior to first dose of study drug) transient ischemic attack or stroke.
 
8. CTCAE (v5.0) Grade <math>\geq 2</math> hearing loss.
 
9. CTCAE (v5.0) Grade <math>\geq 2</math> neuropathy.
 
10. Have clinically significant cardiac disease including any of the following:
 

Known congestive heart failure requiring treatment (New York Heart Association Grade <math>\geq 2</math>), LVEF <math>< 50\%</math> or local lower limit of normal as determined by MUGA scan or echocardiogram (ECHO), or uncontrolled hypertension (refer to the European Society of Cardiology and European Society of Hypertension guidelines [Williams et al 2018]).

Presence of Common Terminology Criteria for Adverse Events (CTCAE) v5.0 Grade <math>\geq 2</math> ventricular arrhythmias, atrial fibrillation, bradycardia, or conduction abnormality.

Unstable angina pectoris or acute myocardial infarction <math>\leq 3</math> months prior to first dose of study drug.

QTcF <math>> 470</math> msec (males and females). Note: If the QTcF is <math>> 470</math> msec in the first ECG, a total of 3 ECGs separated by at least 5 minutes should be performed. If the average of these 3 consecutive results for QTcF is <math>\leq 470</math> msec, the participant meets eligibility in this regard.

Known history of congenital long QT syndrome.

 
11. Has serious and/or uncontrolled preexisting medical condition(s) that, in the judgment of the investigator, would preclude participation in this study (for example, interstitial lung disease, severe dyspnea at rest or requiring oxygen therapy, severe renal impairment [e.g. estimated creatinine clearance <math>< 30\text{ml/min}</math>], history of major surgical resection involving the stomach or small bowel, or preexisting Crohn's disease or ulcerative colitis or a preexisting chronic condition resulting in baseline Grade 2 or higher diarrhea).
 
12. Prior therapy with any mitogen-activated protein kinase (MEK) or FGFR inhibitor. Prior therapy is defined as a therapeutic dosing, as determined by the Investigator.
 
13. Are currently receiving or are planning to receive during participation in this study, treatment with agents that are known strong inducers or inhibitors of CYP3A4 and medications which increase serum phosphorus and/or calcium concentration. Participants are not permitted to receive enzyme-inducing anti-epileptic drugs, including carbamazepine, phenytoin, phenobarbital, and primidone.

--	--

A Phase 0 Study of Infigratinib in Recurrent Glioblastoma Patients  
 Protocol 2020-08

	
14. Current use of coumarin-derived anticoagulant for treatment, prophylaxis or otherwise. Therapy with heparin, low molecular weight heparin (LMWH) or fondaparinux is allowed.
 
15. Have any known hypersensitivity to gemcitabine, cisplatin, calcium-lowering agents, infigratinib, or their excipients.
 
16. Treatment with another investigational drug or other intervention within 30 days prior to enrollment or within 5 half-lives of the investigational product, whichever is longer.
 
17. Have consumed grapefruit, grapefruit juice, grapefruit hybrids, pomegranates, star fruits, pomelos, Seville oranges or products containing juice of these fruits within 7 days prior to first dose of study drug.
 
18. Have used medications known to prolong the QT interval and/or are associated with a risk of Torsades de Pointes (TdP) 7 days prior to first dose of study drug.
 
19. Have used amiodarone within 90 days prior to first dose of study drug

Phase:	0
Description of Sites/Facilities Enrolling Participants:	Up to 3 U.S. Sites will enroll participants for this study
Description of Study Intervention:	Phase 0: 125 mg of infigratinib administered orally for 7 days prior to surgical resection.  Expansion Cohort: 125 mg of infigratinib administered orally for 21 days of a 28-day treatment cycles.
Study Duration:	Approximately 30 months
Participant Duration:	Phase 0: up to approximately 2 months (screening window of 28 days through Day 30 phone call follow up).  Expansion Cohort: infigratinib will be taken by the participant as long as the drug is tolerated and the investigator believes the participant may be obtaining benefit. Treatment will be taken by the participant until confirmed progression or end of treatment.  All participants will be followed for survival.
Statistical Considerations	The trial is a phase 0 trial and therefore no formal statistics is planned. Historically, the Ivy Center operates on 400 recurrent high-grade glioma patients per year. If 5% of the patients carrying FGFR3 fusion or FGFR1/3 mutations, we expect 20 patients to be eligible for study each year. Assuming 50% patient capture, we envision 10 patients per year to be enrolled in the trial. The duration of the trial is therefore designed to be 24 months with an additional 6 months for clinical follow-up of participants enrolled into expansion cohort (estimated at 50% of the Phase 0 cohort)

A Phase 0 Study of Infigratinib in Recurrent Glioblastoma Patients  
Protocol 2020-08

1.2 SCHEDULE OF ACTIVITIES (SOA)

Procedures	Phase 0							Expansion				Safety Phone Call ~30 days after last dose	Survival Follow Up Phone Call / Letter
	Screening Day -28 to -1	Enrollment/Baseline Day 1	Days 2-5	Pre-surgical Assess. Day 6	Surgical Visit Day 7	Post-op Follow Up ~7 days after last dose	Cycle 1 (28 days) 	Cycle 2 (28 days) 	Subsequent Cycles (28 days) 	End of Study Treatment			
Visit #	1	2	n/a	3	4	5	6-8	9-11	12, 13...	Last	n/a	n/a	
Informed consent	X												
Collect archival/biopsy tissue	X												
Demographics	X												
Medical history	X												
Diagnosis and extent of cancer	X												
Eligibility	X	Pre											
Concomitant medication review	X			X-----X									
Adverse event review and evaluation	X			X-----X							X		
Surgical and medical procedures	X			X-----X									
Phone Call / Letter											Phone	~Q3 months 	
TREATMENT/DRUG ADMINISTRATION													
Administer study drug		QD	QD (Home)	QD	QD		X 	X 	X 				
Review of Home Dosing Diary		X		X	X		1	1	1	X			
Drug Compliance / Accountability		X		X	X		1	1	1	X			
CLINICAL PROCEDURES													
Physical exam	X 										X		
Neurological exam	X 										X		
Brief Physical and Neurological exam						X	1	1	1				
Ophthalmologic Evaluation 	X 					X			C3D1 and every 4 months after	X			
ECOG	X	X				X	1	1	1				
Vital signs	X 			X		X	1	1	1	X			

A Phase 0 Study of Infigratinib in Recurrent Glioblastoma Patients

Protocol 2020-08

	Phase 0								Expansion			Survival Follow Up Phone Call / Letter
	Screening Day -28 to -1	Enrollment/Baseline Day 1	Days 2-5	Pre-surgical Assess. Day 6	Surgical Visit Day 7	Post-op Follow Up ~ 7 days after last dose	Cycle 1 (28 days) 	Cycle 2 (28 days) 	Subsequent Cycles (28 days) 	End of Study Treatment		
Procedures												
Height	X 											
Weight	X 									X		
12-Lead ECG 	X	X		X			1	1	1	X		
Craniotomy					X							
LAB PROCEDURES												
Hematology (CBC w/diff) 	X 						X	1	1	1	X	
Serum chemistry 	X 						X	1	1	1	X	
Pregnancy test 	X 						X	1	1	1	X	
Coagulation 	X 											
Urinalysis 	X 						X	1	1	1	X	
Pharmacokinetic (PK) blood sample		Pre			X 		1, 8, 15	1, 8, 15				
Pharmacokinetic (PK) CSF sample					X 							
Pharmacokinetic (PK) tumor sample					X 							
Pharmacodynamic (PD) blood sample		Pre										
Pharmacodynamic (PD) tumor sample	Archival/ biopsy				X 							
Pharmacogenomic (PG) tumor tissue	Archival/ biopsy											
Patient Derived Xenograft (PDX) tumor sample					X 							
IMAGING PROCEDURES												
MRI – Brain with/without contrast	X 					X 	MRI Q3 months 		Last			
RANO						X	Q3 months		Last			
ADMINISTRATIVE PROCEDURES												
Complete Case Report Forms (CRFs)	X	X		X	X	X	X	X	X	X	X	X
1. Expansion Cohort: study drug administration is every day (QD) 3 weeks on/ 1 week off 2. Screening assessment may be completed at D1 pre-dose, if completed at screening, does not need to be repeated at D1 pre-dose except for ECG and ECOG. Results must be available to confirm eligibility prior to dosing.												

A Phase 0 Study of Infigratinib in Recurrent Glioblastoma Patients

Protocol 2020-08

Procedures	Phase 0						Expansion				Safety Phone Call ~30 days after last dose	Survival Follow Up Phone Call / Letter
	Screening Day -28 to -1	Enrollment/Baseline Day 1	Days 2-5	Pre-surgical Assess. Day 6	Surgical Visit Day 7	Post-op Follow Up ~7 days after last dose	Cycle 1 (28 days) 	Cycle 2 (28 days) 	Subsequent Cycles (28 days) 	End of Study Treatment		

3. Single ECG. At Screening: If the QTcF is >470 msec in the first ECG, a total of 3 ECGs separated by at least 5 minutes should be performed. If the average of these 3 consecutive results for QTcF is ≤470 msec, the participant meets eligibility in this regard.
 
4. See Section 8.2.12.
 
5. Serum pregnancy test (women of childbearing potential) at screening. Urine pregnancy test (women of childbearing potential) at remaining visits pre-dose (if applicable).
 
6. PK blood samples will be obtained on D1 pre-dose and on D7 at pre-dose (trough level), 0.5, 1, 2, 4, 6, 8, 24 (trough) hours post dose (<math>\pm</math>5 min window for 0.5hr and 1hr; <math>\pm</math>15min window for 2, 4, 6hr; <math>\pm</math>1hr for 8 and 24 hours post dose).
 
7. PK CSF, Tumor and blood samples will be collected intra-operatively at approximately 8 hours post-dose (<math>\pm</math>1 hour)
 
8. PD/PDX Tumor sample will be collected intra-operatively at approximately 8 hours post-dose (<math>\pm</math>1 hour)
 
9. MRI completed as Routine Care. At screening, utilize the most recent MRI available. At follow-up, utilize the first MRI obtained post-operatively.
 
10. The start of follow up for long-term survival begins following completion of the Day 30 safety follow up call.
 
11. Ophthalmic exam should include visual acuity testing (including corrected distance acuity), slit lamp examination of the anterior eye segment, intraocular pressure (IOP), retinal OCT and dilated fundoscopy. Additional examinations such as specular microscopy and corneal pachymetry will be performed as clinically indicated. In addition, ophthalmic exams should be done as clinically indicated.
 
12. A visit window of <math>\pm</math>1 day in Cycle 1 and 2 on Days 1, 8, and 15 and <math>\pm</math>3 days in Cycle 3 onward is allowed.
												

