#### 6.1.2 DOSING AND ADMINISTRATION

In Phase 0, the dose for infigratinib will be 125 mg oral (PO), taken QD over 7 days on Day 1 through Day 7. The last dose will be given on the morning of Day 7, approximately 7-9 hours prior to craniotomy for tumor resection. Day 1 and Day 7 doses will be taken in the clinic. Days 2-5 will be taken at home. Day 6 will be taken at home or in clinic (Table 2).

**Table 2** Phase 0 Dose Schedule

Study Intervention	infigratinib
Day 1	125 mg In Clinic
Day 2	125 mg At Home
Day 3	125 mg At Home
Day 4	125 mg At Home
Day 5	125 mg At Home
Day 6	125 mg At Home or Clinic
Day 7	125 mg In Clinic

In the Expansion Cohort, the dose for infigratinib will be 125 mg oral (PO) QD on Days 1 through 21 in a 28-day cycle. On days with a trough PK sample, the doses will be administered in clinic, if possible (Cycle 1 & 2, Days 1, 8, and 15). A delay of a cycle due to holiday, weekend, bad weather, or other unforeseen

A Phase 0 Study of Infigratinib in Recurrent Glioblastoma Patients  
Protocol 2020-08

circumstances will be permitted for a maximum of 7 days and not counted as a protocol deviation. The reason for the treatment interruption should be documented on the CRF. A cycle begins when study treatment is dispensed for the cycle and administered. Thus, if an expected cycle start is delayed, the number of days in the current cycle is increased beyond 28 days. A visit window of  $\pm 1$  day in Cycle 1 and 2 on Days 1, 8, and 15 and  $\pm 3$  days in Cycle 3 onward is allowed.

A participant may continue to receive study treatment until confirmed progressive disease, unacceptable toxicity, or discontinuation for any other reason.

Participants should be instructed to take the daily dose of infigratinib in the morning in a fasted state at least at least 1 hour before or 2 hours after a meal. Infigratinib should be taken at approximately the same time each day (24  $\pm$  2 hours interval). Subjects should be instructed to swallow the capsules whole, i.e., without chewing, with a glass of water (~250 mL), which should be consumed over as short a time as possible.

If vomiting occurs after ingestion of a daily dose, no re-dosing of the participant should occur before the next scheduled dose. Also, if a dose cannot be administered early in the day, that dose should not be made up later that day, and dosing should resume the following day.

---

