##### 8.1.1.1 PK BLOOD SAMPLES COLLECTION

Participants will donate approximately a total of fifteen 4mL blood samples (approximately 60mL of blood) as noted in Section 1.2. If intravenous vein (IV) blood collection is utilized, the approximate total volume of blood will be 120mL of blood. Venipuncture may cause some pain, bleeding or bruising where the needle entered the participant's body. Some participants may have an intravenous (IV) catheter placed or a midline catheter for blood collection, as determined needed by the investigator. Placing an IV may cause some pain, and bleeding or bruising at the spot where the needle entered the participant's body. There may also be a risk of irritation of the vein (phlebitis), infection, blood clot, leakage or infiltration and/or nerve or tendon injury during insertion. Care will be taken to avoid these problems. The longer an IV catheter is left in place, the more common it is for redness or infection to develop. This information will be included in the participant informed consent and discussed with the participant as needed

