### 8.2.12 LABORATORY EVALUATIONS

Blood will be obtained and sent to the local laboratory for a CBC/hematology, blood chemistry, and pregnancy test as noted in the below table.

Table 9 Clinical laboratory parameters collection plan

Test Name	Test Category
Hematology	Hgb, platelets, white blood cells (WBC), red blood cells (RBC), differential (basophils, eosinophils, lymphocytes, monocytes, neutrophils [% or absolute])
Blood Chemistry	Albumin, amylase (or lipase), ALT, AST, bicarbonate, calcium, chloride, creatinine, total bilirubin, direct bilirubin (only if total bilirubin is ≥ grade 2), blood urea nitrogen (BUN), potassium, sodium, random or fasting glucose, alkaline phosphatase, total protein, magnesium, phosphorus Calculated or measured creatinine clearance
Urinalysis	Macroscopic panel (dipstick) (bilirubin, blood, glucose, ketones, WBC, pH, protein, specific gravity) Reflexive Microscopic panel (RBC, WBC, casts)
Pregnancy test	At screening visit, serum pregnancy test At subsequent cycles, urinary pregnancy test.
Coagulation	International normalized ratio (INR) and pro-thrombin time (PT) or Quick Test; activated partial thromboplastin time (PTT)

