#### 8.2.12.2 CLINICAL CHEMISTRY

Blood chemistry assessments of the parameters listed in [Table 9](#) will be tested as per the Schedule of Activities.

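### In the Expansion Cohort, in-cycle serum chemistry is scheduled on Day 1 only, so the first-week phosphorus/calcium check has no scheduled draw and the related dose rules have no scheduled on-drug result

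*Combined protocol and SAP*

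**What the plan says.** **Dosing.** Section 1.2, footnote 1: "Expansion Cohort: study drug administration is every day (QD) 3 weeks on/ 1 week off". Section 6.1.2 agrees: 125 mg daily on Days 1 to 21 of 28.

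**Chemistry schedule.** The SoA row "Serum chemistry 4" (the 4 is a footnote mark pointing to Section 8.2.12) has entries at screening, at the visit headed "Post-op Follow Up ~7 days after last dose" and at End of Study Treatment. It has a plain 1 for each of Cycle 1, Cycle 2 and subsequent cycles. Section 8.2.12.2 adds no days; it says that the parameters "will be tested as per the Schedule of Activities". The Table 9 panel contains calcium and creatinine, and its list ends "alkaline phosphatase, total protein, magnesium, phosphorus".

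**Visits that already exist.** The PK blood row shows Days 1, 8 and 15 in Cycles 1 and 2. Footnote 12 allows a window of plus or minus one "day in Cycle 1 and 2 on Days 1, 8, and 15", and three days from Cycle 3. Section 6.1.2: "On days with a trough PK sample, the doses will be administered in clinic, if possible". From Cycle 3 the SoA has one visit per cycle.

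**What the text asks for.** Section 6.4.1.3.3 wants phosphorus and calcium checked in the first week of Expansion treatment, and close attention to electrolytes and early renal signs, without naming days. Table 4 titrates sevelamer by phosphorus band. It also holds and then reduces infigratinib if phosphorus exceeds 7.0 mg/dL after 14 or more days of phosphorus-lowering therapy. Table 3 has hold, reduce or discontinue rules for phosphorus, calcium and creatinine.

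**The concern.** The protocol manages dose on laboratory values that the drug is known to move, but the only scheduled in-cycle chemistry falls where a drug effect is least likely to show. Cycle 1 Day 1 is the first Expansion dosing day. Every later Day 1 follows an off-drug week. Section 6.4.1.3.3 describes raised phosphate as a pharmacodynamic effect of the drug. It also provides for pausing the binder in the off week when phosphate is no longer raised, so the protocol foresees phosphate settling just before the next scheduled draw. The same section reports serious renal events.

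Two things are at stake. The first is safety management: up to three sites must decide for themselves when to do the first-week check, and an asymptomatic rise during dosing may prompt no for-cause test. The second is endpoint 2e, laboratory abnormalities per CTCAE. Section 8.3.1 keeps laboratory abnormalities that are not clinically significant out of the adverse event record, so for those the endpoint depends on the draws taken.

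**Working it through.** **1. Do plain numbers in the SoA mean cycle days?** The protocol gives one count that tests this. Section 8.1.1.1: "Participants will donate approximately a total of fifteen 4mL blood samples", about 60 mL.
- Phase 0 Day 1 pre-dose: 1
- Phase 0 Day 7 pre-dose, 0.5, 1, 2, 4, 6, 8 and 24 h: 8
- Expansion Cycles 1 and 2 on Days 1, 8 and 15: 2 × 3 = 6
- Total: 1 + 8 + 6 = 15 samples, and 15 × 4 mL = 60 mL. This reproduces the stated figure.

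With one draw per Expansion cycle the total would be 1 + 8 + 2 = 11. So the numbers are cycle days, and a lone 1 means Day 1.

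**2. Which columns hold the chemistry entries?** In the extracted table the chemistry row sits one column to the right of the ECG and vital-sign rows. Read literally, it would put a blood draw in the safety phone-call column. Aligned with the brief-exam and vital-sign rows, it gives the post-op visit, Day 1 of each cycle, and End of Study Treatment. The alignment is a reconstruction, but neither reading yields a Day 8 or Day 15 panel.

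**3. Days off drug at each scheduled panel.** The last dose is on Day 21, and the next Day 1 is Day 29 counted from the start of the current cycle.

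| Panel | Calculation | Days after last dose |
|---|---|---|
| Nominal | 29 − 21 | 8 |
| Cycle 2, ±1 day | 28 − 21 to 30 − 21 | 7 to 9 |
| Cycle 3 onward, ±3 days | 26 − 21 to 32 − 21 | 5 to 11 |
| Permitted 7-day cycle delay | 36 − 21 | 15 |

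The post-op panel is also about 7 days after the last Phase 0 dose.

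**4. Coverage in Cycles 1 and 2.**
- Dosing days after Day 1: 2 × (21 − 1) = 40
- Scheduled chemistry panels on those days: 0
- Scheduled PK blood visits on those days: 2 × 2 = 4
- Interval between panels now: 29 − 1 = 28 days
- With chemistry on Days 1, 8 and 15: 8 − 1 = 7, 15 − 8 = 7 and 29 − 15 = 14 days

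Trough draws on Days 8 and 15 would follow 7 and 14 doses.

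**5. Text against schedule.** The first-week check has only the Cycle 1 Day 1 panel inside Days 1 to 7. That is the first dosing day, and the SoA does not state the draw time relative to the dose. The next scheduled panel is Cycle 2 Day 1, 28 days later and off drug.

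**The case against.** The strongest reply is that on-drug testing is already instructed. Section 6.4.1.3.3 asks for the first-week check. Table 4 requires creatinine at least weekly once it is raised together with hyperphosphatemia. Table 3 applies throughout a cycle. This stands in part: a reader might infer that there is no on-drug monitoring at all, and the documents do not support that. What is missing is a scheduled draw, because the text names no day and Section 8.2.12.2 sends the site to an SoA with no matching entry.

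Four further limits stand.
- A reader might infer that Table 4's 14-day rule requires a draw at Day 15. It does not. It is a condition that any later result can meet, and Table 3 holds drug at >7.0–10.0 mg/dL despite phosphate-lowering therapy without a 14-day minimum. Timing a draw to the hours of sevelamer exposure is also weakly founded: Table 4 starts sevelamer on Cycle 1 Day 1, but Section 6.4.1.3.3 only permits prophylactic binders.
- A reader might try to size the loss from Table 3's branches for resolution within or beyond 7 days. Those are dosing rules, not recovery data. Phosphorus is given up to 14 days to resolve, so some elevations would still show on Day 1, and a value that has fallen to Grade 1 is under-graded rather than lost.
- No section asks for mid-cycle hematology, although its SoA row has the same pattern.
- First-week, for-cause and End of Study Treatment results recover some events, and the last may fall on drug.

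The drug's safety profile, which would inform how often to sample, is left to the Investigator's Brochure and partly redacted.

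**Conclusion.** The point holds as a mismatch between schedule and text with a safety consequence. In-cycle chemistry falls on the first dosing day or about 8 days off drug. The first-week phosphorus/calcium check has no SoA entry. The phosphorus, calcium and creatinine rules have no scheduled on-drug result, apart from unscheduled or for-cause tests. In Cycles 1 and 2 this means 0 scheduled panels over 40 dosing days, against 4 existing blood-draw visits.

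The conclusion rests on the column alignment and on reading plain numbers as cycle days; the second is confirmed by the fifteen-sample count. The effect on endpoint 2e is real in direction but unknown in size, and no under-recording rate can be derived. It touches one part of a descriptive secondary endpoint in about 10 participants (20 × 50%, Section 9.2). Primary endpoints are unaffected. The case for amending rests mainly on safety management and the low cost.

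**What to change.** Amend the SoA as follows.
- Change serum chemistry (the Table 9 panel, with phosphorus, calcium and creatinine) from Day 1 to Days 1, 8 and 15 in Cycles 1 and 2, drawn with the existing PK blood.
- State that the Cycle 1 Day 8 visit serves the Section 6.4.1.3.3 check, and should be held on Day 7 where possible. Day 7 is inside the one-day window and within the first seven days; Day 9 would be late.
- Keep the existing one-day window for Day 15.
- Hematology on the same days is optional.

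No dose or management rule changes. The cost is about 4 visits × 10 participants = 40 extra tube sets (80 if all 20 entered the Expansion Cohort), with no new visits. The downsides are slightly more blood drawn and more laboratory abnormalities recorded. The gap from Cycle 3 onward remains, because closing it would need an extra visit per cycle. A bare SoA footnote pointing to Section 6.4.1.3.3 would cure the missing entry for the first-week check, but would give the other dose rules no scheduled on-drug result.
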